#### 4.3.2 OPEN / IWRS User Requirements

OPEN/IWRS users must meet the following requirements:

- Have a valid CTEP-IAM account (*i.e.*, CTEP username and password).
- To enroll patients or request slot reservations: Be on an ETCTN Corresponding or Participating Organization roster with the role of Registrar. Registrars must hold a minimum of an AP registration type.
- To approve slot reservations or access cohort management: Be identified to Theradex as the “Client Admin” for the study.
- Have regulatory approval for the conduct of the study at their site.

Prior to accessing OPEN/IWRS, site staff should verify the following:

- All eligibility criteria have been met within the protocol stated timeframes.
- If applicable, all patients have signed an appropriate consent form, and HIPAA authorization form.

#### 4.4 General Guidelines

Following registration, patients should begin protocol treatment within 7 days. Issues that would cause treatment delays should be discussed with the Principal Investigator. If a patient does not receive protocol therapy following registration, the patient's registration on the study may be canceled. The Study Coordinator should be notified of cancellations as soon as possible.

### 5. TREATMENT PLAN

#### 5.1 Agent Administration

Treatment will be administered on an outpatient basis. Reported adverse events and potential risks are described in [Section 7](#). Appropriate dose modifications are described in [Section 6](#). No investigational or commercial agents or therapies other than those described below may be administered with the intent to treat the patient's malignancy. The patient will be requested to maintain a medication diary of each dose of medication. The medication diary will be returned to clinic staff at the end of each course.

##### 5.1.1 AZD1775 administration

AZD1775 is an oral drug that should be ingested 2 hours before a meal or 2 hours after a meal. Capsules should not be broken, crushed or chewed. Missed doses should not be made up, resume dosing with the next scheduled dose. If vomiting occurs shortly after dosing, the dose should not be repeated. Patients will be instructed to bring all unused capsules and their medication diary (refer to Appendix D) to each study visit for assessment of compliance.

The study will have a dose escalation phase to determine the provisional recommended phase II dose. Once the recommended phase II dose is determined, a dose expansion will be performed. AZD1775 will be administered only during the first five weeks of treatment concurrently with external beam whole pelvis radiotherapy and concurrent cisplatin. It will not be continued beyond five weeks during brachytherapy or the delivery of additional external beam radiotherapy.

#### Dose Escalation

A cohort of 3 patients per dose level are planned:

- The starting dose will be dose level (DL) 1, AZD1775 will be administered on Day 1, 3, and 5 of each week
- If AZD1775 is tolerable at DL1 with no DLT experienced, 3 patients enter DL2.
- If AZD1775 is tolerable at DL2 with no DLT experienced, 3 patients enter DL3.
- If AZD1775 is tolerable at DL3 with no DLT experienced, 3 patients enter DL4 of which AZD1775 will be administered Day 1-5 of the week.

If the first 2 patients enrolled in a starting dose level (DL1) experience DLT, further enrollment

to that dose level will stop and a lower dose level will be explored. If the first 2 patients enrolled in the lower dose level (DL-1) experience DLT, further enrollment to that dose level will stop. The Principal Investigator will discuss with the sponsors regarding the appropriate next step.

If 1/3 patients encounter a dose-limiting toxicity (DLT), then the cohort will be expanded to 6 patients. If  $\geq 2/6$  of patients encounter DLT, then that dose level will be declared excessively toxic. A total of 6 patients will be entered into the previous dose level.

The recommended phase II dose (RPTD; also called the MTD) is defined as the dose level with  $\leq 1/6$  patients with DLT.

### **Dose Expansion**

If excessive toxicity is not observed after exploring all dose levels, dose level 4 will be declared as the provisional RPTD. Then 12 additional patients will be enrolled (make up to a total of 15 patients).

If 1/3 patients encountered DLT, then the cohort will be expanded to 6 patients.

If  $\leq 1/6$  patients encountered DLT, that dose level is declared as the RPTD, and 9 additional patients will be enrolled (make up to a total of 15 patients).

If  $\geq 2/6$  of patients encounter DLT, then that dose level will be declared excessively toxic. Additional 3 patients will be entered into the lower dose level. If  $\leq 1/6$  patients at the lower dose level had DLT, then that level will be declared as the RPTD, and 9 additional patients will be enrolled (make up to a total of 15 patients).

Table 5-1: Dose Escalation Schedule

Dose Escalation Schedule			
Dose Level	Dose*		
	Radiation a (fractions)	Cisplatin b (weekly)	AZD1775 c Week 1-5
Level -1	25 days	40 mg/m 	100 mg, oral, QD day 3 and 5 of each week
Level 1	25 days	40 mg/m 	100 mg, oral, QD day 1, 3, 5 of each week
Level 2	25 days	40 mg/m 	150 mg, oral, QD day 1, 3, 5 of each week
Level 3	25 days	40 mg/m 	200 mg, oral, QD day 1, 3, 5 of each week
Level 4	25 days	40 mg/m 	200 mg, oral, QD day 1, 2, 3, 4, 5 of each week

a Radiation: External beam radiation (45-50 Gy) will be administered five days a week for five weeks.  
b Cisplatin can be administered either on Monday or Wednesday once commenced on external beam radiation every week.  
c AZD1775 will be administered on Monday, Wednesday and Friday of each week once commenced on external beam radiation every week.

### 5.1.2 Cisplatin

Cisplatin will be administered as an intravenous infusion at a dose of 40 mg/m^2 week. The time of infusion will be 1 hour ± 15min. The weekly dose should not exceed 70 mg. Five doses of cisplatin will be administered concomitantly with the external beam whole pelvis radiotherapy. Cisplatin will not be continued beyond five weeks during brachytherapy or the delivery of additional external beam pelvic radiotherapy.

### 5.1.3 Radiotherapy

All patients will receive whole pelvis external beam radiotherapy (EBRT) with concurrent cisplatin and AZD1775 for five consecutive weeks. Further radiotherapy may be delivered after five weeks, tailored to the specific disease site, without cisplatin or AZD1775.

Radiotherapy will adhere to the following general guidelines:

- Whole pelvis EBRT will be delivered in a uniform manner during the first five weeks of treatment using conformal, field-based techniques (four coplanar, orthogonal fields), intensity modulated radiation treatment (IMRT) or volumetric modulated arc treatment (VMAT).
- Patient management after the initial five weeks of EBRT/cisplatin/AZD1775 will vary depending on the patient cohort (cervix, upper vagina, uterus, recurrent disease) and treatment response, and may include surgery, brachytherapy, further external beam radiotherapy for residual pelvic disease, or no further treatment. To aid in interpreting

toxicity in this phase I study, detailed reporting of normal tissue radiation dosimetry will be required for the initial course of whole pelvis EBRT and for all subsequent radiotherapy courses (brachytherapy or further external beam radiotherapy) beyond five weeks. Radiotherapy after the initial five weeks will be delivered alone without concurrent cisplatin or AZD1775.

- Patient with newly diagnosed cervical cancer (cT1B-3B, N0/1, M0/1) or upper vaginal cancer (T1-3, N0/1, M0/1) will receive brachytherapy after whole pelvis EBRT/cisplatin/AZD1775 unless otherwise contraindicated.
- Patients with newly diagnosed, unresectable endometrial cancer should be re-evaluated for surgery after whole pelvis EBRT/cisplatin/AZD1775. If surgery is contraindicated, these patients should be considered for brachytherapy unless otherwise contraindicated.
- Patients with pelvic recurrences of cervical or endometrial cancer after previous surgery should be considered for brachytherapy (central pelvic recurrences), further external beam radiotherapy (pelvic sidewall recurrences) or both.

#### 5.1.4 Whole Pelvis External Beam Radiotherapy

Whole pelvis EBRT will be delivered in a uniform manner during the first five weeks of treatment using conformal, field-based techniques (four coplanar, orthogonal fields), intensity modulated radiation treatment (IMRT) or volumetric modulated arc treatment (VMAT). Regardless of the treatment technique, the clinical target volume (CTV) and planning target volume (PTV) should be adequate to ensure coverage of clinical and subclinical primary tumor and lymph node disease extension accounting for inter- and intra-fractional target motion.

- Patients will undergo CT simulation for radiation treatment planning.
- Gross target volume (GTV) delineation: The GTV will encompass the gross primary tumor volume (GTVp), and any grossly enlarged pelvic lymph nodes (GTVn).
- Clinical target volume (CTV) delineation: The CTV will include the GTVp and the GTVn.
  - The GTVp will include the GTV, entire cervix, uterus, parametria and at least the upper half of the vagina. The lower third of the vagina should be included in the GTVp in patients with involvement of the upper vagina, at the discretion of the responsible radiation oncologist.
  - The GTVn will include the internal, external and distal common iliac lymph nodes, the upper pre-sacral lymph nodes anterior to the S1/2 vertebral bodies (GTVn) and the para-aortic lymph nodes (if clinically warranted, at the discretion of the responsible radiation oncologist). Refer to the [RTOG GYN postoperative contouring atlas](#) for lymph node delineation. The GTVn will be obtained by applying a 7 mm margin around the iliac vessels, plus extensions to include any adjacent visible lymph nodes. The presacral nodes will be contoured until the superior border of the S3 vertebral body is reached; below this point the nodal volume will be separated into two structures. The external iliac nodes will be contoured to the superior aspect of the femoral heads. The GTVn will be modified to exclude bone, muscle, and bowel.
- Organs at risk (OAR) delineation: The rectum, sigmoid, small bowel and bladder will be

delineated in all patients. Refer to the [RTOG contouring atlas for normal female pelvic anatomy](#) for OAR delineation.

- Rectum: The outer rectal wall will be contoured from the anus to the level of the sigmoid flexure.
- Sigmoid: The outer sigmoid wall will be contoured from where the rectum ends to the point of connection to the ascending colon laterally. Any sigmoid adjacent or above the uterus should be contoured.
- Small bowel: The peritoneal cavity will be contoured from the axial CT/MR slice 1 cm superior to the upper field border, and will continue to its most inferior extent in the pelvis. Individual loops of bowel should not be contoured separately. Rectum should be contoured separately from bowel.
- Bladder: The outer bladder wall in its entirety will be contoured.
- The external beam pelvic dose will be 45-50 Gy in 25 daily fractions of 1.8-2 Gy. Megavoltage radiotherapy (10 MV or greater) will be used. Treatment will be delivered daily, five fractions per week. The dose will be prescribed to an ICRU reference point in accordance with [ICRU 62](#). All fields will be treated daily.
- Treatment verification using cone-beam CT imaging of soft tissue and bone anatomy will be performed daily on the treatment unit to ensure adequate target coverage and day-to-day reproducibility.
- EBRT dose reporting requirements: The absolute rectum, sigmoid, small bowel and bladder volumes (cm^3), and the percentages of the total delineated organ volumes, receiving  $\geq 50\%$  of the prescribed dose and  $\geq 90\%$  of the prescribed dose.

### 5.1.5 Brachytherapy

- Patient with newly diagnosed cervical cancer (cT1B-3B, N0/1, M0/1) or upper vaginal cancer (T1-3, N0/1, M0/1) will receive brachytherapy after whole pelvis EBRT/cisplatin/AZD1775, unless otherwise contraindicated. Patients with newly diagnosed, unresectable endometrial cancer may be considered for brachytherapy after whole pelvis EBRT/cisplatin/AZD1775 if the disease remains unresectable, unless otherwise contraindicated. Patients with central pelvic recurrences of cervical or endometrial cancer after previous surgery may be considered for brachytherapy after pelvic EBRT/cisplatin/AZD1775, unless otherwise contraindicated.
- Brachytherapy will begin after completion of whole pelvis EBRT/cisplatin/AZD1775 and will be delivered according to the usual practice at the treating institution. However, CT or MR imaging of the pelvis after placement of the brachytherapy applicator(s) with delineation of OARs and reporting of OAR doses must be done to aid in interpreting acute and late toxicity in this phase I study.
- For patients with newly diagnosed cervical, upper vaginal or endometrial cancer, brachytherapy typically will be delivered using an intrauterine applicator with a vaginal ring or ovoids. An intrauterine applicator with a vaginal cylinder may be necessary to encompass vaginal disease. Soft tissue imaging (trans-abdominal ultrasound, CT or MR) will be performed with each insertion to confirm correct positioning of the intrauterine applicator. Treatment planning (including estimation of doses to OARs) will be based on

pelvic CT and/or MR obtained after placement of the applicator. A conventional 2D dose prescription (ICRU 38 Point A) or optimized 3D volumetric planning (GEC-ESTRO recommendations or equivalent) will be allowed. The use of interstitial needles, in addition to an intrauterine/intra-vaginal applicator, is encouraged when required to assure optimal target coverage and dosimetric sparing of OARs. Treatment may be delivered using either a pulsed dose rate (PDR) or high dose rate (HDR) techniques.

- Organs at risk (OAR) delineation for brachytherapy: The rectum, sigmoid, small bowel and bladder will be delineated in all patients using axial CT and/or MR images acquired after each brachytherapy applicator insertion. OAR delineation will conform to GEC-ESTRO (or equivalent) recommendations.
  - Rectum: The outer rectal wall will be contoured from the anus to the level of the sigmoid flexure.
  - Sigmoid: The outer sigmoid wall will be contoured from where the rectum ends to the point of connection to the ascending colon laterally. Any sigmoid adjacent or above the uterus should be contoured.
  - Small bowel: The outer wall of individual small bowel loops within 3-4cm of the uterus or applicator will be contoured.
  - Bladder: The outer bladder wall in its entirety will be contoured.
- Brachytherapy reporting requirements: The following brachytherapy technique and dosimetric parameters will be reported:
  - Brachytherapy technique (PDR, HDR)
  - Total brachytherapy dose and total number of fractions
  - The ICRU 38 rectal and bladder reference point doses for each treatment fraction
  - The absolute brachytherapy dose to the maximally irradiated  $2\text{ cm}^3$  of rectum, sigmoid, bladder and small bowel ( $D_{2\text{cm}^3}$ ) for each treatment fraction

### 5.1.6 External Beam Pelvic Boost Radiotherapy for Residual Disease

Further external beam radiotherapy may be used at the discretion of the responsible radiation oncologist to treat residual pelvic disease not amenable to brachytherapy after the initial five weeks of whole pelvis EBRT/cisplatin/AZD1775. This may include persistently enlarged pelvic lymph nodes in patients with newly diagnosed cervical, upper vaginal or endometrial cancer, or persistent central pelvic or pelvic sidewall disease in patients with recurrence of cervical or endometrial cancer. Highly conformal IMRT or VMAT plans are encouraged to minimize the dose to adjacent OARs and potential for acute and late toxicity. The planning target volume (PTV) should be adequate to account for inter- and intra-fractional target motion.

- Organs at risk (OAR) delineation for external beam pelvic boost radiotherapy: OAR delineation for pelvic boost radiotherapy will adhere to the same guidelines as for whole pelvis EBRT:
  - Rectum: The outer rectal wall will be contoured from the anus to the level of the sigmoid flexure.
  - Sigmoid: The outer sigmoid wall will be contoured from where the rectum ends to the point of connection to the ascending colon laterally. Any sigmoid adjacent or above the uterus should be contoured.
  - Small bowel: The peritoneal cavity will be contoured from the axial CT/MR slice 1

cm superior to the upper field border, and will continue to its most inferior extent in the pelvis. Individual loops of bowel should not be contoured separately. Rectum should be contoured separately from bowel.

- Bladder: The outer bladder wall in its entirety will be contoured.
- External beam pelvic boost radiotherapy dose reporting requirements:
  - External beam pelvic boost total dose and total number of fractions
  - The absolute rectum, sigmoid, small bowel and bladder volumes (cm^3), and the percentages of the total delineated organ volumes, receiving  $\geq 50\%$  of the prescribed dose and  $\geq 90\%$  of the prescribed dose

Table 5-2: Regimen description

Regimen Description for dose level 1-3					
Agent	Premedication; Precautions	Dose	Route	Schedule	Cycle Length
AZD1775	5-HT3 antagonist such as ondansetron 8mg PO daily or granisetron (Kytril) 1mg PO daily prior to AZD1775 on days not receiving cisplatin	** capsule	Oral	Once a day Day 1, 3, 5 of the week for 5 weeks	
Cisplatin	IV hydration, antiemetic and steroid prophylaxis pre-medication as per institutional protocol	Infusion time: 1hour Dilute in 500 ml Normal Saline	IV	Once a week for 5 weeks (day 1 or 3)	42-56 days
Radiotherapy					
External Beam Whole Pelvis Radiotherapy				5 days a week (ideally Monday to Friday) for 5 weeks	
Additional treatment (surgery, brachytherapy or additional pelvic radiotherapy) depending on patient cohort and initial response to radiation/cisplatin/AZD1775				Beginning week 6	

**Doses as appropriate for assigned dose level.
 
Ondansetron can be substituted by any other 5HT3 inhibitor at equivalent doses if ondansetron is not available
					

Regimen Description for dose level 4					
Agent	Premedication; Precautions	Dose	Route	Schedule	Cycle Length
AZD1775	5-HT3 antagonist such as ondansetron 8mg PO daily or granisetron (Kytril) 1mg PO daily prior to AZD1775 on days not receiving cisplatin	200mg capsule	Oral	once a day for 5 days a week (Mon-Fri) for 5 weeks	
Cisplatin	IV hydration, antiemetic and steroid prophylaxis pre-medication as per institutional protocol	Infusion time: 1 hour Dilute in 500 ml Normal Saline	IV	once a week for 5 weeks	42-56 days
Radiotherapy					
External Beam Whole Pelvis Radiotherapy				5 days a week (ideally Monday to Friday) for 5 weeks	
Additional treatment (surgery, brachytherapy or additional pelvic radiotherapy) depending on patient cohort and initial response to radiation/cisplatin/AZD1775				Beginning week 6	
Ondansetron can be substituted by any other 5HT3 inhibitor at equivalent doses if ondansetron is not available					

## 5.2 Definition of Dose-Limiting Toxicity

The dose limiting toxicity period will be considered from week 1 until the end of week 5 +7 days upon completing the chemo-radiation portion of the treatment. All patients evaluable for toxicity will be assessed for DLT. The following treatment related toxicities will be considered Dose-Limiting Toxicities (DLTs)

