### 5.2.2 Non-hematologic DLT

- Grade 4 vomiting, or grade 3 vomiting if persistent for longer than 48 hours despite treatment with granisetron, ondansetron or an equivalent medication.
- Grade 4 diarrhea, or grade 3 diarrhea if persistent for longer than 48 hours despite treatment with loperamide, diphenoxylate/atropine or an equivalent medication.
- Grade 3 or 4 rash
- Other grade 3 or 4 radiotherapy associated acute toxicity
- Interruption of whole pelvis radiotherapy for more than 3 days due to acute treatment toxicity
- Inability to receive at least 3 of the 5 planned doses of cisplatin
- If the patient requires an omission longer than 1 week in the administration of AZD1775 and/or cisplatin
- Any grade 3 or 4 non-hematological toxicity with the specific exception of:
  - Nausea, vomiting, diarrhea, or dehydration (all Grade 3) not optimally treated and/or lasts less than 48 hours.
  - Alopecia (of any grade)
  - Inadequately treated hypersensitivity reactions
  - Clinically non-significant, treatable or reversible lab abnormalities including, but not limited to liver function tests, uric acid, hypokalemia or hypomagnesemia.

[Note: reversible G3 and G4 electrolyte disturbances will be considered those that improve, at least to G2, within 48h when optimally treated]

---

 An adverse event or any delay not related to the study medication will not be considered DLT

Management and dose modifications associated with the above adverse events are outlined in [Section 6](#). Dose escalation will proceed within each cohort according to [Table 5-3](#). Dose-limiting toxicity (DLT) is defined above in [Section 5.2](#).

Table 5-3: Dose escalation schema

Number of Patients with DLT at a Given Dose Level	Escalation Decision Rule
0 out of 3	Enter 3 patients at the next dose level.
$\geq 2$	Dose escalation will be stopped. This dose level will be declared the maximally administered dose (highest dose administered). Three (3) additional patients will be entered at the next lowest dose level if only 3 patients were treated previously at that dose.

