1 out of 3	
Enter at least 3 more patients at this dose level.
 
 
• If 0 of these 3 patients experience DLT, proceed to the next dose level.
 
• If 1 or more of this group suffer DLT, then dose escalation is stopped, and this dose is declared the maximally administered dose. Three (3) additional patients will be entered at the next lowest dose level if only 3 patients were treated previously at that dose.
 

$\leq 1$ out of 6 at highest dose level below the maximally administered dose	
This is generally the recommended phase 2 dose.
 
Once the provisional recommended phase 2 dose is found, 9-12* patients will be enrolled in the expansion cohort to confirm the safety of this dose.
 
*The final number of patients evaluated at the recommended phase 2 dose will be 15:
 
 
• If 3 patients have been previously enrolled during the dose escalation phase, 12 additional patients will be evaluated in the dose expansion phase
 
• If 6 patients have been previously enrolled during the dose escalation phase, 9 additional patients will be enrolled in the dose escalation
 

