#### 11.1.1 Definitions

Evaluable for toxicity. All patients will be evaluable for toxicity from the time of their first treatment with AZD1775, radiotherapy or cisplatin.

Evaluable for objective response. The patients will be assessed for response according to the local investigator.

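### The 3- and 6-patient dose decisions include anyone who has had one treatment, so a patient who stops early for unrelated reasons most naturally counts as DLT-free

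*Combined protocol and SAP*

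**What the plan says.** Section 5.2 sets the DLT period from week 1 to the end of week 5 plus 7 days and fixes who is assessed: "All patients evaluable for toxicity will be assessed for DLT". Section 11.1.1 supplies the definition: "All patients will be evaluable for toxicity from the time of their first treatment with AZD1775, radiotherapy or cisplatin". One radiotherapy fraction with no AZD1775 capsule is therefore enough to enter the set.

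The DLT list opens with "The following treatment related toxicities will be considered Dose-Limiting Toxicities", and footnote 1 adds: "An adverse event or any delay not related to the study medication will not be considered DLT". Three bullets in 5.2.2 concern treatment not delivered:

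- on the number of cisplatin doses, "Inability to receive at least 3 of the 5 planned doses of cisplatin";
- on breaks in radiotherapy, which names its cause, "Interruption of whole pelvis radiotherapy for more than 3 days due to acute treatment toxicity";
- on gaps in either drug, "If the patient requires an omission longer than 1 week in the administration of AZD1775 and/or cisplatin".

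Table 5-3 escalates on 0 of 3, or on 1 of 3 followed by 0 of the next 3. Its instruction after 1 of 3 is "Enter at least 3 more patients at this dose level". After 0 of 3 the next three patients go to the next level.

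Section 5.4 lists withdrawal, intercurrent illness and progression among the reasons to stop treatment. Section 5.1.1 says missed AZD1775 doses are not made up and sets no minimum number. Section 4.4 allows cancellation of a registration only when no protocol therapy was received. Section 13.2 gives a dose-finding maximum of 24 and an overall maximum of 33.

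**The concern.** The recommended phase II dose is the primary objective, and each step toward it rests on 3 or 6 patients. A patient who took one or two capsules and then withdrew for personal reasons has had little chance to show a DLT at that dose, yet fills one of those places. If that patient is counted as DLT-free, a cohort of three gives roughly the information of two while being read as three. The error runs toward the higher dose.

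The gap is narrower than the open definition suggests. Low exposure caused by toxicity is already captured by the three bullets quoted above, so only unrelated causes are affected. Stopping treatment is also not the same as leaving observation. Intercurrent illness ends treatment under 5.4 but is not a reason for removal from study under 5.6, and 5.5 provides an end-of-treatment visit 28 ± 7 days after the last AZD1775 dose and further follow-up. The case with no remaining DLT risk mainly fits very early withdrawal of consent.

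**Working it through.** **Plan's own figure.** Section 13.2 states a maximum of 33. Four dose levels of 6 give 4 × 6 = 24, and 9 expansion patients at a level that already has 6 give 24 + 9 = 33. This reproduces exactly and leaves no place for replacements.

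**Inputs.** The escalation rule is from Table 5-3. The true DLT rate p (30% and 40%) and the share u of patients who stop early for unrelated reasons (5% and 10%) are assumptions, because the documents give neither. Patients are taken as independent, and u applies to both groups of three.

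**Nominal rule.** With q = 1 − p, P(escalate) = q³ + 3pq² × q³.

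- p = 0.30: 0.343 + 0.441 × 0.343 = 0.494
- p = 0.40: 0.216 + 0.432 × 0.216 = 0.309

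**Early leavers counted as DLT-free.** If they carry half the DLT risk, replace p by p(1 − u/2). If they carry none, which is an upper bound, replace p by p(1 − u).

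| True rate | Nominal | u = 5%, half risk | u = 10%, half risk | u = 5%, no risk | u = 10%, no risk |
|---|---|---|---|---|---|
| 30% | 0.494 | 0.510 | 0.525 | 0.525 | 0.557 |
| 40% | 0.309 | 0.326 | 0.343 | 0.343 | 0.378 |

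Example: at p = 0.30, u = 10% and half risk, the effective rate is 0.30 × 0.95 = 0.285 and q = 0.715. Then 0.3655 + 0.4371 × 0.3655 = 0.525.

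**Exactly one early leaver in the first three.** Let r be that patient's DLT probability, with the next three fully exposed. P(escalate) = (1 − r)q² + [r q² + (1 − r)2pq] × q³. At p = 0.30:

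- r = 0.15 (half risk): 0.4165 + 0.4305 × 0.343 = 0.564
- r = 0 (upper bound): 0.49 + 0.42 × 0.343 = 0.634

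**How often this arises.** The chance of at least one such patient in a cohort of three is 1 − 0.95³ = 14% at u = 5% and 1 − 0.90³ = 27% at u = 10%.

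**Size of a replacement allowance.** If all 24 dose-finding places were used and every early leaver needed replacing, 24 / 0.95 = 25.3 and 24 / 0.90 = 26.7. That is about 2 to 3 extra patients after rounding up.

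**The case against.** Three arguments favour leaving the text alone.

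- **Oversight.** Section 12.1 requires the Protocol Principal Investigator to sign off every escalation decision and to hold at least monthly calls with the study investigators and the CTEP Medical Officer(s). Appendix C adds a Data Safety and Monitoring Board. Decisions are central, so inconsistent counting between sites is an unlikely route to a wrong escalation. This stands as a limit on the harm, but none of these bodies is given a written criterion.
- **Visibility and later confirmation.** Section 13.1.1 records discontinuations and interruptions, and the chosen level is taken to 15 patients to confirm safety. A change in P(escalate) at one level is therefore not the same as a change in the chance of a wrong recommended dose. This also stands. The expansion tests the chosen level, however; it does not undo an escalation already made.
- **Room to add patients.** Table 5-3 allows more than three additional patients after 1 of 3. It gives no such room after 0 of 3, which is where an uninformative patient does most to carry the cohort upward.

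A reader might infer something stronger: that the same patient could be scored as a DLT, because the cisplatin-dose bullet and the omission bullet carry no causal wording of their own while the radiotherapy bullet does. Footnote 1 also names only adverse events and delays, not withdrawal. The documents do not support giving this weight. The lead-in "The following treatment related toxicities will be considered Dose-Limiting Toxicities" governs every bullet, footnote 1 reinforces it, and being unable to receive a drug or requiring its omission does not naturally describe a patient who chooses to leave. It is a remote reading that one sentence should close, and no size is claimed for it here.

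**Conclusion.** The point holds in a limited form. A set for DLT assessment is defined, so it would be wrong to say that none exists. The set is too permissive for decisions on 3 or 6 patients: the text available for review sets no minimum AZD1775 exposure, no completion of the window and no replacement. No sentence states how an early leaver is scored. DLT-free is the most natural reading, and it biases the rule toward escalation.

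On half-risk assumptions with 5% to 10% departure, the shift is about 2 to 3 percentage points: 49% to 51-53% at a true rate of 30%, and 31% to 33-34% at 40%. The upper bounds are 53-56% and 34-38%. In a cohort where exactly one of the first three is such a patient, the shift at 30% is larger, from 49% to 56%, or to 63% as the upper bound. All of this depends on the assumed departure rate and remaining risk. Some pages were not available for review, although the governing sections (5.2, 11.1.1, 13.1.1 and 13.2) were. This is a cheap improvement rather than a flaw that undermines the design.

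**What to change.** - **Sections 5.2 and 13.1.1.** Base the 3- and 6-patient decisions on a DLT-evaluable set: patients with a DLT in the window, or patients who completed the window with a minimum AZD1775 exposure that the sponsor states in advance. Doses omitted for toxicity should not count against that minimum.
- **Same sections.** State that a patient who stops for unrelated reasons without a DLT, and does not meet the definition, counts neither as DLT-free nor as a DLT and is replaced for the escalation decision.
- **Section 11.1.1.** Leave it as it is for the safety tables, so that every treated patient is still reported.
- **Section 13.2.** State that the dose-finding maximum of 24 counts DLT-evaluable patients, or add a replacement allowance that the sponsor sets. Leave the expansion count unchanged, since those patients do not enter the 3- or 6-patient decisions.

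The cost is a short wording change, a few replacement patients and some added accrual time.
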